## 12.7. PUBLICATIONS

All data generated in this study will be the property of Dompé farmaceutici S.p.A. Publication of the results by the PI will be subject to mutual agreement between the PI and Dompé farmaceutici S.p.A. The Sponsor agrees that the study results (including negative and inconclusive as well as positive results) can be made publicly available by the Investigator publishing in peer reviewed journals; presenting results at scientific congresses; and posting information and results on internet-based public registers and databases.

In any case, study results will be communicated in full to the related competent authorities for the countries involved by the submission of a complete Clinical Study Report.

As the Sponsor agrees that the study results can be published by the Investigator(s), the Investigator agrees to submit any manuscript (abstract, publication, paper etc.) to the Sponsor before any public disclosure.

This will be done in order to ensure that clinical trial results are reported in an objective, accurate and balanced manner. The Sponsor reviews proposed manuscripts prior to submission within a reasonable period of time (30-90 business days in relation with the complexity of the work).

The Investigator(s) will also be provided by the Sponsor with the clinical study report and the results of any additional analysis, tables, figures etc undertaken for the purposes of the article, in order to take responsibility for the content of the publication(s).

On an exceptional basis, the Sponsor may temporarily delay registration of certain data elements (e.g. compound, name, outcome, measures etc.) to seek necessary intellectual property protection. This is because early disclosure of such a data could, in some circumstances, prevent or negatively impact patentability.

# 14.3 APPENDIX 3 AMERICAN-EUROPEAN CONSENSUS CRITERIA FOR SJÖGREN'S SYNDROME

Reference: Vitali C, et al. Classification criteria for Sjogren's syndrome: a revised version of the European criteria proposed by the American-European Consensus Group. Ann Rheum Dis 2002; 61:554-558.

In order to make a diagnosis of Sjögren's syndrome, the following criteria must be met:

#### I. Ocular Symptoms (at least one)

- Symptoms of dry eyes for at least 3 months
- A foreign body sensation in the eyes
- Use of artificial tears 3 or more times per day

#### II. Oral Symptoms (at least one)

- Symptoms of dry mouth for at least 3 months
- Recurrent or persistently swollen salivary glands
- Need for liquids to swallow dry foods

#### III. Ocular Signs (at least one)

- Abnormal Schirmer's test, (without anesthesia;  $\leq 5 \text{ mm/5 minutes}$ )
- Positive vital dye staining of the eye surface

#### **IV. Histopathology**

• Lip biopsy showing focal lymphocytic sialoadenitis (focus score  $\geq 1$  per 4 mm2)

#### V. Oral Signs (at least one)

- Unstimulated whole salivary flow ( $\leq 1.5$  mL in 15 minutes)
- Abnormal parotid sialography
- Abnormal salivary scintigraphy

#### VI. Autoantibodies (at least one)

• Anti-SSA (Ro) or Anti-SSB (La), or both

#### For a primary Sjögren's syndrome diagnosis:

- Any 4 of the 6 criteria, must include either item IV (Histopathology) or VI (Autoantibodies)
- Any 3 of the 4 objective criteria (III, IV, V, VI)

#### For a secondary Sjögren's syndrome diagnosis:

• In patients with another well-defined major connective tissue disease, the presence of one symptom (I or II) plus 2 of the 3 objective criteria (III, IV and V) is indicative of secondary SS.

#### **Exclusion Criteria**

- Past head and neck radiation treatment
- Hepatitis C infection
- Acquired immunodeficiency syndrome (AIDS)
- Pre-existing lymphoma
- Sarcoidosis
- Graft versus host disease
- Current use of anticholinergic drugs

# Abbreviations

| ADR    | Adverse Drug Reaction                        |
|--------|--|
| AE     | Adverse Event                                |
| ANCOVA | Analysis of Covariance                       |
| ATC    | Anatomical Therapeutic Chemical              |
| BCDVA  | Best Corrected Distance Visual Acuity        |
| BDRM   | Blind Data Review Meeting                    |
| CsA    | Cyclosporine A                               |
| CSR    | Clinical Study Report                        |
| eCRF   | electronic Case Report Form                  |
| ENR    | Enrolled set                                 |
| EU     | European Union                               |
| FAS    | Full Analysis set                            |
| KFR    | Key First efficacy Results                   |
| IDEEL  | Impact of dry eye on everyday life           |
| IMP    | Investigational Medicinal Product            |
| MAR    | Missing at Random                            |
| MCMC   | Markov chain Monte Carlo                     |
| MedDRA | Medical Dictionary for regulatory activities |
| MI     | Multiple Imputation                          |
| MI-RD  | Multiple Imputation using retrieve dropouts  |
| MMRM   | Mixed Model for Repeated Measurements        |
| MNAR   | Missing Not at Random                        |
| NEI    | National Eye Institute                       |
| PP     | Per protocol set                             |
| PT     | Preferred Term                               |
| rhNGF  | recombinant human Nerve Growth Factor        |
| RND    | Randomized set                               |
| SAE    | Serious Adverse Event                        |
| SAF    | Safety set                                   |
| SANDE  | Symptom Assessment in Dry Eye                |
| SAP    | Statistical Analysis Plan                    |
| SEM    | Standard error of the mean                   |
| SOC    | System Organ Class                           |
| TEAE   | Treatment Emergent Adverse Event             |
| TFBUT  | Tear Film Break-Up Time                      |
| TID    | Ter in die (three times a day)               |
| US     | United States                                |
|        |  |

# 1. Revision History

Table 1: Revision history

| Document Version | Changes Made  | Document Date |
|------------------|---------------|---------------|
| Final 1.0        | First release | 31 March 2023 |

# 2. Introduction

This document outlines the statistical methods to be implemented in the analysis of the data of NGF0221 Clinical Trial. The purpose of this plan is to provide general guidelines from which the analysis will proceed, containing a more technical and detailed elaboration of the principal features of the analysis described in the protocol. Any changes to the protocol or Case Report Form (CRF) may necessitate updates to the Statistical Analysis Plan (SAP). In case of deviations from this updated SAP, explanations will be provided in the Clinical Study Report (CSR).

This SAP is based on study protocol Version No. 5.0 - 16 June 2022 [1], Patient diary Version No. 3.0 - 07 February 2022 [2] and Case Report Form Version No. MSC004 - 02 March 2023 [3].

# 3. Study Design

# 3.1 General design and plan

This is a 4-weeks phase III, multicenter, double-masked, vehicle-controlled clinical study to evaluate safety and efficacy of cenegermin ophthalmic solution at 20 mcg/mL solution versus vehicle, in patients with severe Sjogren's dry eye disease under treatment with Cyclosporine A (Cyclosporine A or other topical ophthalmic treatment of the same class).

### 3.2 Study Objectives and endpoint

The study objective is to assess the efficacy and safety of cenegermin ophthalmic solution at 20 mcg/mL concentration administered three times daily for 4 weeks in patients with severe Sjogren's dry eye disease under treatment with Cyclosporine A (CsA).

#### 3.2.1 Primary

| Objective(s)   | Endpoint(s)   |
|--|---|
| • To compare the efficacy of cenegermin vs.
vehicle in Schirmer I test (without anesthesia)
>10mm/5min at week 4 by testing the
superiority.          | • Schirmer I test (without anesthesia) >10mm/5min at week 4.                  |
| • To compare the efficacy of cenegermin vs. vehicle in Symptom Assessment in Dry Eye questionnaire (SANDE) global score at week 12 by testing the superiority. | • Change from baseline in SANDE global score at week 12                       |
| 3.2.2 Secondary  |   |
| Objective(s)   | Endpoint(s)   |
| • To compare the efficacy of cenegermin vs. vehicle in Schirmer I test at week 4, 8, 12 and 16 by testing the superiority.                                     | • Change from baseline in Schirmer I test [Time frame: week 4, 8, 12 and 16]. |

# Objective(s)

- To compare the efficacy of cenegermin vs. vehicle in Cornea and conjunctiva vital staining with fluorescein (National Eye Institute [NEI] scales) at week 4, 8, 12 and 16 by testing the superiority.
- To compare the efficacy of cenegermin vs. vehicle in Tear Film Break-Up Time (TFBUT) at week 4, 8, 12 and 16 by testing the superiority.
- To compare the efficacy of cenegermin vs. vehicle in SANDE scores at week 8, 12 and 16 by testing the superiority.
- To compare the efficacy of cenegermin vs. vehicle in worsening in symptom scores (SANDE) and/or NEI score at week 4 by testing the superiority.
- To compare the efficacy of cenegermin vs. vehicle in impact of dry eye on everyday life (IDEEL) questionnaire at week 4, 8, 12 and 16 by testing the superiority.

# 3.2.3 Exploratory

#### Objective(s)

- To evaluate the use of preservative free artificial tears use during the treatment period.
- To evaluate the use of preservative free artificial tears use during the treatment period.
- To compare the efficacy of cenegermin vs. vehicle in Schirmer I test at week 2 by testing the superiority.
- To compare the efficacy of cenegermin vs. vehicle in SANDE scores at week 2 and 4 by testing the superiority.
- To compare the efficacy of cenegermin vs. vehicle in Cornea and conjunctiva vital staining with fluorescein (NEI scale) at week 2 by testing the superiority.
- To compare the efficacy of cenegermin vs. vehicle in TFBUT at week 2 by testing the superiority.
- To compare the efficacy of cenegermin vs. vehicle in worsening in symptom scores (SANDE) and/or NEI score at week 2 by testing the superiority.

# Endpoint(s)

- Change from baseline in Cornea and conjunctiva vital staining with fluorescein (NEI scale) [Time frame: week 4, 8, 12 and 16].
- Change from baseline in TFBUT [Time frame: week 4, 8, 12 and 16].
- Change from baseline in SANDE global scores, and for severity and frequency [Time frame: week 8, 12 and 16].
- Number of patients experienced a worsening in symptom scores (SANDE global score) and/or NEI score ≥ 50% assessed at week 4.
- IDEEL questionnaire [Time frame: week 4, 8, 12 and 16].

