#### 3.3.1. Rationale for Selection of dose, control group and treatment schedule in the study

The dose proposed in this study (cenegermin 20 mcg/mL) has already been tested both in heathy volunteers for five consecutive days (CCI and a patients affected by several ocular surface diseases, including moderate to severe DE (CCI and a patients).

Cenegermin 20 mcg/mL (one drop in each eye six times daily for 8 weeks), was also tested in the Phase I/II studies in NK (CCI ), DE (CCI ) and in patients after cataract and refractive surgery (CCI ).

Cenegermin 20 mcg/mL (one drop in each eye TID for 8 weeks) was also tested in the Phase II study (CCL) in moderate to severe DE.

Cenegermin 20 mcg/mL administered TID, demonstrated to be safe and well tolerated (**CC**), will also ensure the lubrification of the ocular surface in the present study where the use of artificial tears will be not allowed during the treatment period, according to the Investigator.

Higher doses of rhNGF (up to 180 mcg/mL) were administrated to patients with diseases of the back of the eye, such as retinitis pigmentosa (Study CCL) for up to 168 days.

The 20 mcg/mL concentration of cenegermin is well sustained by the current manufacturing process and is used in a commercial formulation.

A dose regimen of a drop TID of cenegermin ophthalmic solution and a treatment duration of 4 weeks has been selected based on the results of the previous clinical trials described above.

The administration of a total of 3 drops per day for both the study arms has been chosen to guarantee to patients randomized to the vehicle arm to have the minimum amount of lubrication that is compatible with symptoms' relief. A double-blind study design was adopted to minimize systematic bias. Randomization is expected to minimize patient selection bias and increase baseline comparability between treatment groups. The use of placebo control is critical to the study design, providing an accurate estimate of the additive benefit of pharmacotherapy.

The use of the drug's vehicle as placebo helps in making the latter as indistinguishable from the cenegermin solution.

Patients with insufficient therapeutic response, tolerability issues, or worsening of symptoms may be discontinued at any time during the study.

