# 6.3. EARLY WITHDRAWAL FROM THERAPY OR ASSESSMENT

## 6.3.1. Primary Reason For Discontinuation From The Study

A premature discontinuation will occur when a patient who signed the ICF ceases participation in the study, regardless of circumstances, before the completion of the study protocol procedures. Patients can be prematurely discontinued from the study for one of the following reasons:

- Adverse event (AE): Any significant AE that, is not compatible with study continuation especially relating to tolerability of IMP.
- Disease progression or worsening, that is not compatible with study continuation especially when indicative of insufficient therapeutic response based on clinical signs or worsening of symptoms after 2 weeks of treatment.
- **Death**.
- **Lost to follow-up** (Every effort must be made to contact the patient; a registered letter must be sent).
- ▶ Non-compliance with study drug: an indication that a patient has not agreed with or followed the instructions related to the study medication.

- Severe Protocol violation: an event or decision that stands in contrast to the guidelines set out by the protocol.
- Study terminated by the Sponsor: an indication that a clinical study was stopped by Sponsor.
- **Withdrawal of consent**: study discontinuation requested by a patient for whatever reason.
- Other reasons, such as administrative reasons, pregnancy, ocular trauma or surgery, inability to travel for follow-up appointments.

Before removal, each case should first be discussed with Dompé farmaceutici S.p.A. Anyway, a subject may withdraw from the study at any time at his or her own request.

The reasons for premature discontinuation from the study will be reflected on the Study Termination Record of the eCRF. Unless the patient has withdrawn consent, the follow up visit assessments should be performed as detailed in § 6.

The investigator should advise patients that prematurely discontinue on any therapies or treatments for their condition and refer them for further treatment as appropriate

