#### **Study discontinuation**

For any patient discontinuing the study following randomization, the Investigator will:

- ask the patient to undergo, as far as possible, a final medical visit (Early Termination Visit ETV) to examine the patient's health conditions. This examination will verify that all values tested at screening have remained within a clinically acceptable range (i.e., not clinically significant changes compared to screening).
- > arrange for alternative medical care of the withdrawn patient, if necessary.
- report in the eCRF date and time of the last dose administration, and date and primary reason of study discontinuation.
- record in the eCRF any follow-up if the patient is withdrawn for an AE. AE's should be followed until resolution.

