#### 7.8 Handling of missing and incomplete data

All reasonable efforts will be made to reduce the rate of missing data. Investigators will be trained about the importance of patient retention and full data capture. Also, any reasonable attempts should be made by the investigators to emphasize continued subject's participation for the full duration of the trial.

Patients who discontinue the treatment will not be withdrawn from the study by default but will be asked to complete safety and efficacy observations as per the protocol, unless otherwise they withdraw their consent. Patients who discontinue study treatment and decide to remain in the study

by following the schedule of assessments and continuing to adhere to protocol requirements are defined as "retrieved drop-out" patients.

For the primary and key secondary analyses, missing data will be handled by means of Multiple Imputation using retrieve dropouts (MI-RD), as detailed in sections 10.1.2 and 10.2.2.

In addition, to further minimize missing data, if a patient cannot refer to the site for a planned followup visit, the investigator will try to obtain any relevant information from the patients, including documents/laboratory results available from local medical care.

The number of subjects with missing data will be presented under the "Missing" category. Missing values will not be included in the denominator count when computing percentages. When continuous data will be summarized, only the non-missing values will be evaluated for computing summary statistics.

For the analyses of parameters for which an independent blinded reading center may be involved per protocol, the following rules will be used:

- 1. If assessment from blinded reading center is available, such value will be used for the analysis.
- 2. If assessment form blinded reading center is not available, the corresponding evaluation (if any) from the site investigator will be used.
- 3. If both assessments (blinded reading center and site investigator) are not available, a statistical imputation method will be applied as described in this SAP.

Rules for handling missing data of IDEEL questionnaire are reported in section 12.3, according to the dedicated manual.

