#### 10.2.3 Descriptive Analysis

Independently of results on primary and key secondary endpoints, descriptive in nature analyses will be performed on all secondary endpoints (section 3.2.2) at each available timepoints by means of descriptive statistics.

In case of continuous measures, analyses will be provided for baseline visit, each post-baseline visit, and their change from baseline. Comparisons between treatments will be performed using twosample t-test (assuming unequal variances) or, if the required assumptions are not met, the two-

sample Mann–Whitney U test will be used. Assumption of normal distribution of endpoints for continuous data will be assessed by a visual inspection of distribution.

In case of categorical variables, shift tables versus baseline will be summarized for all post-baseline visits, and the Fisher's Exact test will be performed.

The following graphical representations will be provided by treatment:

- Schirmer I test Observed Mean (±SEM) and Mean change from baseline (±SEM) at each timepoint.
- Observed percentage of patients with Schirmer I test >10mm/5min at each timepoint.
- SANDE global score Observed Mean (±SEM) and Mean change from baseline (±SEM) at each timepoint.
- Cornea and conjunctiva vital staining total score Observed Mean (±SEM) and Mean change from baseline (±SEM) at each timepoint.
- TFBUT Observed Mean (±SEM) and Mean change from baseline (±SEM) at each timepoint.

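### Patients withdrawn for worsening who have no week-4 value leave both the numerator and the denominator of the week-4 worsening endpoint

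*SAP*

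**What the plan says.** **Endpoint.** SAP 3.2.2 lists "Number of patients experienced a worsening in symptom scores (SANDE global score) and/or NEI score ≥ 50% assessed at week 4", with a superiority objective attached. It is a status at one visit (day 28 ± 2).

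**Leaving the study.** Protocol 6.3.1 makes disease progression or worsening a reason for discontinuation, "especially when indicative of insufficient therapeutic response based on clinical signs or worsening of symptoms after 2 weeks of treatment". Protocol 3.3.1 is wider: "Patients with insufficient therapeutic response, tolerability issues, or worsening of symptoms may be discontinued at any time during the study".

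**After leaving.** Under Protocol 6.3.1 the investigator advises such patients and is to "refer them for further treatment as appropriate". Under Protocol 6.3.2 the investigator is to "arrange for alternative medical care of the withdrawn patient, if necessary". The same sections ask for follow-up assessments unless consent is withdrawn, and keep patients who stop only the treatment in the study by default.

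**Analysis.** The endpoint is not among the key secondary endpoints in SAP 10.2.1. SAP 7.8 specifies multiple imputation for primary and key secondary analyses. For the rest, "Missing values will not be included in the denominator count when computing percentages", although the number missing is displayed. SAP 10.2.3 applies: "In case of categorical variables, shift tables versus baseline will be summarized for all post-baseline visits, and the Fisher's Exact test will be performed". SAP 4.4 assigns data to the visit at which they were collected. SAP 7.2.4 uses values regardless of intercurrent events.

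**The concern.** Worsening is both the event to be counted and a listed reason for not being present to be counted. The protocol names the period after 2 weeks of treatment, and the endpoint is read at week 4, so the window for this loss lies just before the assessment. A patient withdrawn in that window with no week-4 SANDE or NEI value is treated like any other missing patient.

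Such missingness is informative and tends to understate worsening within an arm. If more patients are lost this way in one arm than in the other, the arm comparison is distorted too, in either direction. This is the trial's dedicated count of deterioration, so a reader of Table 14.2.5.3 could take the rate at face value.

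**Working it through.** **1. Trace the rules for a patient withdrawn for worsening between week 2 and week 4.**

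| Situation at week 4 | Treatment under the SAP |
|---|---|
| Value observed at the visit, with or without other treatment before it | Used as observed (SAP 7.2.4) |
| No week-4 value, but an early-exit value | Not stated |
| No week-4 and no early-exit value | Out of numerator and denominator (SAP 7.8) |

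The second row is open because the protocol is inconsistent. The synopsis (study procedures) and the visit list in Protocol section 6 pair early exit with week 4. The visit table in Protocol 6.2 places the Early Termination Visit with Visit 7, whose listed procedures include neither SANDE nor NEI. Protocol 6.3.2 describes a final visit that checks the values tested at screening, which would include both. These passages must be reconciled. SAP 4.4 maps no early-exit value to week 4.

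**2. Check whether imputation reaches the endpoint.** It does not. Table 14.2.5.3 carries no multiple-imputation label, unlike the key secondary tables. SAP 7.8 promises an imputation method for reading-centre parameters when both readings are absent, but the SAP describes none for this count.

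**3. Size within one arm (illustration).** The documents give no rate of worsening and no rate of withdrawal for worsening. Inputs taken from them are 80 enrolled at 1:1, so 40 per arm, and a 10% dropout allowance, 80 × 0.10 = 8 patients. Assumed: r = 4 patients seen to worsen at week 4, w patients withdrawn for worsening with no week-4 value, and no other missing data.

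- Available-case rate = r / (40 − w)
- Rate with the w patients counted as worsened = (r + w) / 40

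| w | Available case | Counted as worsened |
|---|---|---|
| 0 | 4/40 = 10.0% | 4/40 = 10.0% |
| 1 | 4/39 = 10.3% | 5/40 = 12.5% |
| 2 | 4/38 = 10.5% | 6/40 = 15.0% |
| 4 | 4/36 = 11.1% | 8/40 = 20.0% |
| 8 | 4/32 = 12.5% | 12/40 = 30.0% |

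The last row puts the whole dropout allowance in one arm and is an extreme. The gap runs from 0 to 30.0 − 12.5 = 17.5 percentage points.

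**4. Size of the arm contrast (illustration).** Assumed: 4 observed worseners on vehicle and 2 on cenegermin, and 8 withdrawals for worsening split as shown. Differences are vehicle minus cenegermin, with two-sided Fisher p-values.

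| Withdrawn, vehicle / cenegermin | Available case | Counted as worsened |
|---|---|---|
| 4 / 4 | 4/36 − 2/36 = 5.6 points (p = 0.67) | 8/40 − 6/40 = 5.0 (p = 0.77) |
| 6 / 2 | 4/34 − 2/38 = 6.5 (p = 0.41) | 10/40 − 4/40 = 15.0 (p = 0.14) |
| 8 / 0 | 4/32 − 2/40 = 7.5 (p = 0.40) | 12/40 − 2/40 = 25.0 (p = 0.006) |
| 2 / 6 | 4/38 − 2/34 = 4.6 (p = 0.68) | 6/40 − 8/40 = −5.0 (p = 0.77) |
| 0 / 8 | 4/40 − 2/32 = 3.8 (p = 0.69) | 4/40 − 10/40 = −15.0 (p = 0.14) |

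Balanced losses leave the contrast nearly unchanged. Unbalanced losses can shrink it or hide a reversal.

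**5. The right-hand columns are upper bounds.** A withdrawal for worsening need not meet the 50% threshold. Taking 50% as relative to baseline, a SANDE global score on a 100 mm scale cannot rise by half from a baseline above 100/1.5 = 66.7. A total staining score with maximum 15 + 18 = 33 cannot do so from above 33/1.5 = 22.

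**The case against.** A reader might infer that every clear case of worsening is lost, either through a missing visit or because the patient is re-measured after other treatment. The documents do not support that:

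- Withdrawal for worsening is permitted, not required, and patients who worsen and stay are counted.
- Patients who stop only the treatment remain under assessment, and follow-up visits are requested unless consent is withdrawn.
- An early-exit value taken before other care may exist.
- Other treatment before week 4 is possible but not certain. SAP 7.8 defines retrieved drop-outs as still adhering to protocol requirements, and Protocol 5.6 generally bars other ophthalmic medication.

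A reader might also infer that the gap hides harm. It would not do so on its own. Protocol 8.2 has clinically relevant untoward changes in study parameters or questionnaire responses reported as adverse events. SAP 8.3 and 11.1 tabulate discontinuation reasons, and adverse events leading to discontinuation, by arm. Week-4 NEI change is a key secondary endpoint with imputation. Week-2 worsening is an exploratory endpoint, although Appendix 15.1 lists no table for it.

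These points limit the number affected and the consequence. They do not supply a rule for the patient with no week-4 value, and none of the other outputs feeds into this count.

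**Conclusion.** The gap is real and narrow. Under SAP 7.8 and 10.2.3, a patient withdrawn for worsening with no week-4 value leaves the count because of the event being counted, and no early-exit rule prevents it. The direction within an arm is towards understating worsening, provided that at least some of these patients would have met the threshold. The effect on the arm contrast depends on balance: about half a point in the balanced example, and 17.5 points (25.0 against 7.5) in the most unbalanced vehicle example. All of these rest on assumed counts, because the true number is unknown and could be zero.

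The endpoint is descriptive and outside the hierarchy. Neither the co-primary result nor the familywise error rate is affected. The point is worth correcting because the repair is cheap, not because the trial's conclusion depends on it.

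**What to change.** Amend SAP 3.2.2, 10.2.3 and the shell of Table 14.2.5.3 before unblinding:

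1. Keep any observed week-4 value as observed, in line with the treatment-policy approach.
2. Reconcile the early-exit and Early Termination Visit passages (synopsis; Protocol section 6, 6.2 and 6.3.2). State that an early-exit SANDE or NEI value collected before week 4 is used when week 4 is missing.
3. When week 4 is missing, count the patient as worsened if the recorded reason for study discontinuation is disease progression or worsening, or if the last available post-baseline SANDE global or NEI score is at least 50% worse than baseline.
4. Label this count as a composite and state its denominator. Show patients missing for other reasons by arm and reason, rather than scoring them as not worsened without comment. Report the observed-case count alongside.

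The cost is a few lines of SAP text and one table shell. Week-2 scores and discontinuation reasons are already collected. The downside is that the composite relies partly on the investigator's stated reason, which is recorded masked but need not meet the 50% threshold. That is why the label and the observed-case count are needed.
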